7.3.5 Baseline Covariates (Aim 1, Aim 2, and Further Aim)

Clinical characteristics will be measured during the pre-ILD baseline and pre-index baseline periods unless otherwise specified.

7.3.5.1 Demographic Characteristics

- **Index year**—The year of the patient’s fibrosing ILD diagnosis date or index date will be identified.
- **Age**—Age will be defined as of the index year.
- **Age groups**—Patients will be assigned to one of the following age groups: 18–44, 45–64, and 65+.
- **Sex**—Sex will be captured from enrollment data; patients with undefined gender will be removed from the study sample
- **Race/ethnicity**—Patients will be classified as Hispanic, non-Hispanic White, non-Hispanic Black, non-Hispanic Asian, Other/Unknown. This variable depends on the

availability of data within the sociodemographic data and will be missing for some patients.

- **Insurance type**—Payer type will be defined as commercial, Medicare, Medicaid.
- **Geographic region**—The U.S. region in which the patient is enrolled in a health plan will be described. States will be categorized into geographic regions in accordance with the U.S. Census Bureau's region designations. The five health plan regions are presented in Table 2.

Table 2. Health Plan Regions

Region	State
Northeast	CT, MA, ME, NH, RI, VT, NJ, NY, PA
Midwest	IL, IN, MI, OH, WI, IA, KS, MN, MO, ND, NE, SD
South	DC, DE, FL, GA, MD, NC, SC, VA, WV, AL, KY, MS, TN, AR, LA, OK, TX
West	AZ, CO, ID, MT, NM, NV, UT, WY, AK, CA, HI, OR, WA
Other	Armed Forces, American Samoa, Federated State of Micronesia, Guam, Marshall Islands, Commonwealth of the Northern Mariana Islands, Puerto Rico, Palau, Virgin Islands

7.3.5.2 Clinical Characteristics

- **Underlying ILD type**—Patients will be classified into the following underlying ILD types based on claims from the entire study period: autoimmune ILD, HP, sarcoidosis, unclassified ILD/IIP, and multiple. The underlying ILD type will be defined based on the presence of ≥ 1 specific ICD-10-CM diagnosis code for autoimmune ILD, HP, and sarcoidosis. Patients without any underlying ILD diagnosis will be classified into the unclassified ILD/IIP type. Patients with diagnoses for >1 underlying ILD types will be classified as multiple.
- **Respiratory diseases**—Separate indicator variables will be created for the presence of ≥ 1 diagnosis code in any position on a medical claim. The following conditions will be included: pulmonary hypertension, acute respiratory failure, asthma, COPD, pneumonia, lung transplantation, upper respiratory tract infection, lower respiratory tract infection, lung cancer, and cystic fibrosis.
- **Other clinical characteristics** – Similar to respiratory disease, a separate indicator variables will be created for the presence of ≥ 1 diagnosis code in any position on a medical claim. The following conditions will be included: gastroesophageal reflux disease (GERD), heart failure, and obstructive sleep apnea.
- **Quan-Charlson comorbidity score**—A comorbidity score will be calculated based on the presence of diagnosis codes on medical claims.^{10, 11} The Quan-Charlson comorbidity score will also be categorized into the following groups: zero, one to two, three to four, and five or more.
- **Comorbid conditions**—General comorbid conditions will be defined using the Clinical Classifications Software managed by the Agency for Healthcare Research and Quality (AHRQ).¹² This measure generates indicator variables for specific disease

conditions based on ICD-9-CM and ICD-10-CM diagnoses. The top 20 comorbid conditions will be presented.

[figure not shown]
- **Smoking**—An indicator variable will be created to identify patients with evidence of current or prior tobacco use based on diagnosis codes or pharmacy fills for smoking cessation treatments (bupropion, varenicline tartrate, or nicotine [inhalation, gum, lozenge, transdermal]).
- **Pulmonary rehabilitation**—Indicator and count variables will be created for the presence of procedure codes for pulmonary rehabilitation.

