date (i.e., similar to the matched oxygen therapy patient in time from the fibrosing ILD diagnosis date to the index date, and during the same continuous enrollment period as the fibrosing ILD diagnosis date).

NOTE: Following review of results from Aim 1, the study team will determine whether continuous enrollment criteria for Aim 2 and Further Aim requires revision.

Variables:	
Aim 1
 
Outcomes: time to initiation of oxygen therapy; time to sustained oxygen therapy use; sustained oxygen therapy use within the first 12 months of follow-up
 
Baseline covariates: demographic characteristics (age, sex, race/ethnicity, geographic region, insurance type, index year), clinical characteristics (underlying ILD type; respiratory diseases; other clinical characteristics; Quan-Charlson comorbidity score; Agency for Health Research and Quality [AHRQ] comorbid conditions; smoking; pulmonary rehabilitation) healthcare utilization characteristics (provider specialty; medication use; all-cause HCRU; all-cause health care costs)
 
Stratification: IPF vs non-IPF ILD
 
Aim 2 [REDACTED]
 
Exposure: oxygen therapy vs no oxygen therapy
 
Primary Outcomes: Time to disease progression; time to all-cause mortality; time to hypoxemia, time to acute exacerbations, counts of acute exacerbations
 
[REDACTED]
 
Baseline covariates: demographic characteristics (index year, age, sex, race/ethnicity, geographic region, insurance type), clinical characteristics (underlying ILD type; respiratory diseases; other clinical characteristics; Quan-Charlson comorbidity score; AHRQ comorbid conditions; smoking; pulmonary rehabilitation) healthcare utilization characteristics (provider specialty; medication use; all-cause HCRU; all-cause health care costs)

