7. RESEARCH METHODS

7.1 STUDY DESIGN

[figure not shown]
This is a non-interventional study of patients enrolled in a commercial, Medicaid, or Medicare plan, using existing administrative claims and EHR data in Optum's Market Clarity Integrated Claims + Clinical database for the period of 01 October 2015 through 30 June 2022 (study period). The study period may be extended through latest data available at the time of study implementation to increase study sample.

To describe the initiation and use of oxygen therapy after first fibrosing ILD diagnosis (**Aim 1**), patients aged ≥ 18 years with newly diagnosed fibrosing ILD will be identified from 01 October 2016 through 30 June 2022 (patient identification period). A schematic of the observation and identification periods is presented in Figure 1. Patients will be required to have 12 months of baseline continuous enrollment prior to fibrosing ILD diagnosis for collecting patient demographics and clinical characteristics. The pre-ILD baseline period will also be used to describe baseline prevalence of oxygen therapy use. Patients will be followed for a variable period from the fibrosing ILD diagnosis date (Section 7.2.2) until the earlier of disenrollment from the health plan, end of study period, or death. Oxygen therapy use will be described, and results will be stratified by underlying cause of fibrosis (e.g., IPF vs non-IPF ILD). Factors associated with initiation of oxygen therapy will be assessed using multivariable methods.

To assess the impact of oxygen therapy use on outcomes (**Aim 2 and Further Aim**), patients with fibrosing ILD who initiated oxygen therapy will be propensity score matched to those who did not yet initiate oxygen therapy. A schematic of the observation and identification periods is presented in Figure 2. The index date will be defined as the date of oxygen therapy initiation for oxygen therapy cohort, or a date that is eligible for index and is similar to the

[figure not shown]
matched case's index date for no oxygen therapy cohort. Disease progression, acute exacerbations, health care resource utilization (HCRU), and health care costs in the Aim 2 follow-up period will be described and compared between matched cohorts. Outcomes will be modelled using multivariable methods.

Figure 1. Observation and Identification Periods: Aim 1

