Age/age groups	X		X		X	
Race/ethnicity	X		X		X	
Sex	X		X		X	
Insurance type	X		X		X	
Geographic region	X		X		X	
Clinical characteristics						
Underlying ILD type‡	X		X		X	
Respiratory diseases	X		X		X	
Smoking	X		X		X	
Quan-Charlson comorbidity score	X		X		X	
AHRQ comorbid conditions	X		X		X	
Smoking	X		X		X	
Pulmonary rehabilitation	X		X		X	
Healthcare utilization characteristics						
Provider specialty	X		X		X	
Medication use	X		X		X	
All-cause HCRU and costs	X		X		X	

*As available among the subset of patients with information from both EHR and claims

†Measured as of the index date, or first available claim after the index date with value values for each of the characteristics

‡Measured using claims from the entire study period

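### Underlying ILD type is listed as a baseline covariate but is assigned from claims over the whole study period, so it depends on survival, enrollment and care after baseline

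*Combined protocol and SAP*

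**What the plan says.** The abstract's covariate lists for Aim 1 and for Aim 2 both include "clinical characteristics (underlying ILD type; respiratory diseases; other clinical characteristics; Quan-Charlson comorbidity score". Section 7.3.5 sets the general window: "Clinical characteristics will be measured during the pre-ILD baseline and pre-index baseline periods unless otherwise specified". Underlying ILD type is an explicit exception. Section 7.3.5.2 states "Patients will be classified into the following underlying ILD types based on claims from the entire study period". Table 1 in Section 7.3 marks the variable in both baseline columns, with the footnote "Measured using claims from the entire study period".

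The rule has three parts:

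- A specific type needs at least one "specific ICD-10-CM diagnosis code for autoimmune ILD, HP, and sarcoidosis".
- With no such code, "Patients without any underlying ILD diagnosis will be classified into the unclassified ILD/IIP type".
- Patients with codes for more than one of the "underlying ILD types will be classified as multiple".

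Section 7.1 defines the data window as "for the period of 01 October 2015 through 30 June 2022 (study period". Follow-up ends at disenrollment, death or the end of that period. All-cause mortality from the index date is a primary Aim 2 outcome (Section 7.3.3.1).

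**The concern.** A single later code moves a patient out of the unclassified group, and a code for a second type moves the patient into the multiple group. The longer a patient lives and stays enrolled, the more chances there are for such a code. Patients who die early tend to remain unclassified, so the category carries information about the outcome.

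If the variable enters a model, its hazard ratio mixes any real effect of type with time available for coding. If it enters the propensity score, patients are matched partly on events after the index date. Section 7.8 describes the matching as being on baseline variables. It does not mention this dependence, and no baseline-only definition of type appears in the visible text.

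**Working it through.** The plan gives no figure on this point to reproduce, so the check is an illustration.

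**From the documents.** Identification runs from 01 October 2016 to 30 June 2022, so potential follow-up is 0 to 5.75 years. A 12-month baseline is required before diagnosis. One code is enough for a type. Observation stops at death, disenrollment or 30 June 2022.

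**Assumed, because the documents give no values.** First type-specific code at a constant rate λ of 0.3, 0.7 or 1.5 per year, starting 12 months before diagnosis. 40% of patients truly codable. Death 0.1 to 0.3 per year, disenrollment 0.2 per year, oxygen initiation 0.25 per year. Runs were made with and without a shared log-normal frailty (SD 1) acting on death and oxygen initiation. True type has no effect on either event.

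**Step 1: chance that a codable patient is typed.** With t years of follow-up this is 1 − exp(−λ(1 + t)). For λ = 0.3 and t = 3 it is 1 − exp(−1.2) = 0.70.

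| λ per year | t = 0 | t = 1 | t = 3 | t = 5 |
|---|---|---|---|---|
| 0.3 | 26% | 45% | 70% | 83% |
| 0.7 | 50% | 75% | 94% | 99% |
| 1.5 | 78% | 95% | 99.8% | about 100% |

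Classification rises with follow-up at every rate, most visibly when codes arrive slowly.

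**Step 2: null hazard ratio for death, classified v unclassified.** Each setting had 200,000 simulated patients, with entry uniform over 5.75 years, time counted from diagnosis, and a Cox model with type as the only covariate. The true ratio is 1.

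| λ per year | Whole-period type |
|---|---|
| 0.3 | 0.66 to 0.70 |
| 0.7 | 0.76 to 0.79 |
| 1.5 | 0.91 to 0.92 |

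With type taken from the 12-month baseline only, the ratio was 0.98 to 1.01 throughout. The share classified fell from 19–38% to 10–31%.

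**Step 3: null hazard ratio for oxygen initiation (Aim 1).** In the same runs the whole-period type gave 0.94 to 1.02, and about 0.91 to 1.02 over the wider set of assumptions tried. Distortion is smaller here because coding time continues after initiation. If coding triples once oxygen starts, the ratio rises to about 1.3 at λ = 0.3. Baseline-only type returned it to about 1.

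**Step 4: oxygen v no oxygen (Aim 2).** Exposure was made independent of type, with death 0.2 per year, code rate 0.1 to 0.7 per year, and a true oxygen rate ratio of 1, 1.5 or 2. Stratifying on whole-period type moved the oxygen ratio by 0.6% or less; for example 1.991 became 1.980, and 1.980/1.991 = 0.994. Runs with modest confounding by type moved it by at most a few percent in most settings. The direction varied, and baseline-only type sometimes left more residual confounding.

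**The case against.** The strongest reply is that the window is deliberate and disclosed. Underlying cause is largely a fixed attribute, and a later code may record disease already present at baseline. Discarding it loses true information and may weaken confounding control. This stands as a reason to keep the whole-period type in a secondary role. It does not remove the dependence on survival.

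Several stronger readings are tempting but unsupported:

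- *The plan adjusts for or matches on this variable.* The Aim 1 Cox list in Section 7.6.1.3 is a list of possible covariates and does not name underlying ILD type. The matching procedure, which Section 7.2.3 places in Section 7.6.2.2, is not visible. Use in either is possible but not shown.
- *Death rates by type are distorted more than twofold.* That follows only if coding starts at diagnosis and every patient is codable (0.11–0.12 v 0.23–0.32 deaths per year at slow code rates). The required 12-month baseline counts toward typing, and unclassified is a genuine category. No visible aim estimates this contrast.
- *Unequal follow-up mismatches the pairs.* Section 7.3 gives matched pairs the same follow-up duration. That does not cap the window used for typing, so it is no cure, but the simple form of the argument fails.
- *The plan contradicts itself.* Section 7.3.5 allows stated exceptions, and this is one.

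**Conclusion.** The point holds as a design weakness, conditional on ILD type entering a model or propensity score. The existence of the dependence follows from the definition; its size does not, because the documents contain no code, death or disenrollment rates.

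The effect falls mainly on hazard ratios for ILD type itself. For death, the false protective ratio of about 0.66 to 0.92 is timed from diagnosis and assumes a 12-month look-back and 40% codable. If most types are coded around diagnosis, the truth lies near the weak end. For oxygen initiation, distortion is slight unless coding intensifies after oxygen starts. A reader might infer that the Aim 2 comparison of oxygen with no oxygen is materially biased. The checks do not support that, although they do not cover every confounding structure.

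**What to change.** In any model or propensity score, assign underlying ILD type from codes dated on or before the fibrosing ILD diagnosis date for Aim 1, and on or before the index date for Aim 2. Use all available look-back, not only the 12-month baseline. Amend Section 7.3.5.2 and the Table 1 footnote, and state where ILD type is used.

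Keep the whole-period type for description. For Aim 2, also run it as a sensitivity analysis, because baseline-only typing can leave more residual confounding.

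The change is one date condition in the programming. Its cost is more unclassified patients, and the number under each definition should be reported. The IPF v non-IPF split in Section 7.2.2 also counts claims over the study period and should be checked for the same dependence.

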7.2 SETTING

7.2.1 Secondary data source selection

The study will use administrative claims and EHR data from Optum's Market Clarity Integrated Claims + Clinical database.

7.2.2 Study population: Aim 1

The analysis for Aim 1 will include patients newly diagnosed with fibrosing ILD during the patient identification period. Patients must meet the following selection criteria to be included in the study:

Inclusion Criteria

- ≥ 2 fibrosing ILD diagnoses in any position on different dates of service, within 365 days of each other, and in the same continuous enrollment period during the patient identification period. The ***fibrosing ILD diagnosis date*** will be defined as the date of the first fibrosing ILD diagnosis. The two fibrosing ILD diagnosis codes can be one of the following combinations:
 - 2 fibrosis codes
 - 1 fibrosis code & 1 ILD code that requires fibrosis code
- ≥ 18 years of age as of the fibrosing ILD diagnosis date
- Continuous enrollment with medical and pharmacy coverage for 12 months prior to the fibrosing ILD diagnosis date (***pre-ILD baseline period***)

Exclusion Criteria

- Fibrosing ILD diagnosis in the 12-month pre-ILD baseline period
- Unknown gender or geographic region

Cohort Assignment

Patients meeting initial selection criteria for Aim 1 will be assigned to cohorts based on known cause of fibrosis:

- **IPF**— ≥ 2 medical claims with diagnosis for IPF in any position during the study period
- **Non-IPF ILD**— < 2 medical claims with diagnosis for IPF during the study period

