7.3.5.3 Healthcare Utilization Characteristics

- **Provider specialty**—A count of unique days with a non-inpatient claim for treatment by provider specialty category (primary care physician [including general/family practice, internal medicine], pulmonology and rheumatology) will be reported.
- **Medication use**—ILD medication use will be captured at the class level, including administrations and prescription fills. The number of prescriptions fills within each class will also be calculated. Treatment categories will include corticosteroids (methylprednisone, prednisone, prednisolone), biologics, (abatacept, denosumab, etanercept, tocilizumab, infliximab, rituximab), calcineurin inhibitors (cyclosporine, tacrolimus), and other immunosuppressants (mycophenolate mofetil, hydroxychloroquine, leflunomide, methotrexate, sulfasalazine, chloroquine phosphate).
- **All-cause HCRU**—HCRU will be calculated for ambulatory visits (physician office and hospital outpatient), emergency department (ER) visits, inpatient admissions, and pharmacy fills.
- **All-cause health care costs**—Health care costs will be presented as standardized costs. Total costs will be calculated and presented in categories of pharmacy costs and medical costs (outpatient, inpatient, professional services). Costs will be adjusted using the annual medical care component of the Consumer Price Index (CPI) to reflect inflation between the date of the claim and the most recent year for which the annual CPI is available.

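### The underlying ILD type covariate has no IPF level, and no other covariate in the public Aim 2 list identifies IPF, so matching on that list would balance IPF only indirectly and in part

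*Combined protocol and SAP*

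**What the plan says.** Section 7.3.5 defines baseline covariates for Aim 1, Aim 2 and the Further Aim together. Under 7.3.5.2, underlying ILD type has five levels: "autoimmune ILD, HP, sarcoidosis, unclassified ILD/IIP, and multiple". A type is assigned from at least one "specific ICD-10-CM diagnosis code for autoimmune ILD, HP, and sarcoidosis". The residual rule reads: "Patients without any underlying ILD diagnosis will be classified into the unclassified ILD/IIP type". Patients with codes for more than one type go to the multiple level. The variable uses claims from the whole study period.

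IPF is defined elsewhere. Section 7.2.2 assigns each Aim 1 patient to an IPF or non-IPF cohort, with IPF requiring at least two "medical claims with diagnosis for IPF in any position during the study period". In the abstract's list of variables, "Stratification: IPF vs non-IPF ILD" stands under Aim 1 only.

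For Aim 2 the abstract lists "clinical characteristics (underlying ILD type; respiratory diseases; other clinical characteristics; Quan-Charlson comorbidity score; AHRQ comorbid conditions; smoking; pulmonary rehabilitation", plus demographic and healthcare utilization characteristics. Section 7.2.3 draws the Aim 2 patients from the Aim 1 population and refers to Section 7.6.2.2 for the propensity score matching. That section is not in the public text.

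**The concern.** The plan treats IPF as the main division of fibrosing ILD. Section 5 names it first among the diseases, Section 7.1 stratifies by it as the cause of fibrosis, and Section 7.2.2 builds cohorts on it. Yet the covariate meant to describe the underlying disease gives no weight to an IPF code. IPF is mostly folded into a residual level and otherwise scattered over the other levels.

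Aim 2 compares oxygen initiators with matched non-initiators on mortality and FVC progression, and Section 7.8 relies on matching to limit bias. If IPF raises both the chance of starting oxygen and the hazard of death or progression, two cohorts could agree on underlying ILD type and still differ in IPF share. The difference would then be read as an effect of oxygen, and a balance table confined to the listed covariates would have no row to reveal it. Section 7.8's caveat about residual or unobserved confounding is a poor answer here, because IPF is coded in the claims and the plan already uses those codes.

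**Working it through.** The plan gives no figure to reproduce on this point. The check has two parts: reading the definitions, then an illustration of size.

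**1. Where an IPF patient lands under 7.3.5.2**

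- No autoimmune, HP or sarcoidosis code: unclassified ILD/IIP, together with every non-IPF patient who also lacks those codes.
- Codes for one of the three types: that type.
- Codes for two or more of the three: multiple.

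An IPF code changes none of these outcomes.

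**2. Whether another listed Aim 2 covariate identifies IPF**

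- Respiratory diseases (7.3.5.2): "pulmonary hypertension, acute respiratory failure, asthma, COPD, pneumonia, lung transplantation, upper respiratory tract infection, lower respiratory tract infection, lung cancer, and cystic fibrosis". IPF is not among the ten.
- Other clinical characteristics: GERD, heart failure and sleep apnea.
- Medication (7.3.5.3): "Treatment categories will include corticosteroids (methylprednisone, prednisone, prednisolone), biologics", then calcineurin inhibitors and other immunosuppressants. Section 5 names two antifibrotics as approved treatment for fibrosing ILD, but no antifibrotic class is listed, so the nearest drug proxy is absent too.
- Table 1: no IPF row.

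None does.

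**3. How much of an IPF imbalance ILD type could remove**

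All inputs are assumptions; none comes from the documents: IPF prevalence 20–35%; 10–30% of IPF patients carrying one of the three other codes; 40–70% of non-IPF patients in unclassified ILD/IIP; oxygen initiation 30–40% in IPF against 20% in non-IPF; IPF mortality HR 1.5–2.0. Controls are reweighted to the oxygen cohort's distribution of type (unclassified versus any other). With p1 and p0 the IPF shares in the oxygen and control cohorts:

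- SMD = (p1 − p0) / √{[p1(1 − p1) + p0(1 − p0)] / 2}
- Confounding factor = [1 + p1(HR − 1)] / [1 + p0(HR − 1)]

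Worked case (prevalence 35%, 10% of IPF with another code, 40% of non-IPF unclassified, initiation 40% versus 20%, HR 2):

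- Before balancing: p1 = 0.35×0.4 / (0.35×0.4 + 0.65×0.2) = 0.14/0.27 = 51.9%; p0 = 0.35×0.6 / (0.35×0.6 + 0.65×0.8) = 0.21/0.73 = 28.8%. SMD 0.48, factor 1.519/1.288 = 1.18.
- IPF share of controls within unclassified: 0.189/0.397 = 47.6%; within the other types: 0.021/0.333 = 6.3%. The oxygen cohort has 0.178/0.27 = 65.9% unclassified and 34.1% other.
- After balancing on type: p0 = 0.659×0.476 + 0.341×0.063 = 33.5%. SMD 0.38, factor 1.519/1.335 = 1.14.

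Over all combinations, the IPF SMD is 0.22–0.48 before and 0.19–0.48 after balancing on type, and the factor is 1.04–1.18 both before and after. Type removes nothing when the share in unclassified ILD/IIP is the same for IPF and non-IPF patients (here 70% each). It would do better if few non-IPF patients were unclassified, a share the documents do not give.

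**4. Simple illustration for mortality**

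Assuming 30% IPF among matched controls and no true oxygen effect:

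| IPF in oxygen cohort | HR 1.5 | HR 2.0 | HR 2.5 |
|---|---|---|---|
| 40% | 1.20/1.15 = 1.043 | 1.40/1.30 = 1.077 | 1.60/1.45 = 1.103 |
| 50% | 1.25/1.15 = 1.087 | 1.50/1.30 = 1.154 | 1.75/1.45 = 1.207 |

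**The case against.** The strongest reply is that the deciding section cannot be seen. Section 7.2.3 sends the reader to 7.6.2.2 for the matching, and the public text does not contain it. Every Aim 2 patient comes from the Aim 1 population, so an IPF flag exists for all of them, and 7.6.2.2 may match on it or include it in the propensity model. On that view, underlying ILD type is a second axis that sits beside the IPF cohort variable, and for Aim 1, which is stratified by IPF, the missing level does no harm. This stands. A reader might infer that IPF is unmatched in Aim 2; the documents do not support that.

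A reader might also infer that nothing listed can balance IPF. That is too strong. Age, smoking, rheumatology and pulmonology visit days, immunosuppressant use, COPD, pulmonary hypertension and ILD type itself may each carry some information on IPF. Section 7.1 also says that outcomes will be modelled with multivariable methods, so matching is not the only adjustment. These routes are indirect, and none of the listed variables identifies IPF.

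The sizes are also open to attack. A 10- to 20-point IPF gap after matching is assumed, and the formula applies the full IPF hazard ratio with no allowance for what correlated covariates already absorb. This stands as well.

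These replies do not answer the definition itself. Section 7.3.5.2 is public, applies to Aim 2, and states a rule that pools IPF with other disease whatever 7.6.2.2 contains.

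**Conclusion.** The point holds for the covariate definition and the visible Aim 2 list. Underlying ILD type has no IPF level, no other listed covariate identifies IPF, and matching on the list would balance IPF only indirectly and in part. Whether the actual match includes IPF status is unknown. This should be fixed, but it is not a demonstrated failure of the Aim 2 comparison.

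The spurious hazard ratio of about 1.04–1.21 shows only what an IPF imbalance of the assumed kind could do. It rests on assumed IPF shares after matching (40–50% versus 30%), an assumed IPF hazard ratio (1.5–2.5) and no correction through other covariates. It should not be read as an estimate of the bias in this study.

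**What to change.** Add an IPF level to underlying ILD type in 7.3.5.2, with a rule for patients who also carry another type's code, or add a separate IPF indicator to the Aim 2 baseline covariates. Include it in the propensity model or match exactly on it, and report its balance between the matched cohorts. If 7.6.2.2 already does this, 7.3.5.2 and the abstract's Aim 2 list should say so.

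Derive the variable from codes up to the index date. The Section 7.2.2 flag should not be carried over unchanged, because it counts IPF claims over the whole study period and so can draw on codes recorded after index.

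The cost is one new derivation and changes of wording in 7.3.5.2, Table 1 and the abstract. Exact matching may lose a few pairs. Some IPF patients not yet coded by index will be classed as non-IPF, so a little imbalance may remain.
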